#### Eligibility

##### Residual Speech Errors (RSE):

Must have persistent speech errors specifically affecting the English rhotic /r/ sound.

- **Perceptual Classification:**  
Must be classified as having *atypical perception* based on a laboratory-developed classification model applied to standardized perception tasks.
- **Language Background:**  
Native speakers of English.
- **Cognitive and Language Proficiency:**  
Must demonstrate adequate nonverbal cognitive and language skills as assessed by standardized tests, including:
  - **Goldman-Fristoe Test of Articulation—Third Edition (GFTA-3):** Assesses articulation of speech sounds.
  - **Clinical Evaluation of Language Fundamentals—Fifth Edition (CELF-5), Recalling Sentences (RS) and Formulated Sentences (FS) subtests:** Evaluates expressive and receptive language functioning, focusing on sentence recall and formulation.
  - **LinguiSystems Articulation Test (LAT):** Measures production of specific speech sounds.

- **Sentence Repetition Task (SRT):** Assesses verbal memory and grammatical processing through sentence repetition.

- **Hearing Screening:**

Must pass an online pure-tone hearing screening at frequencies 1000 Hz, 2000 Hz, and 6000 Hz, at 30 dB intensity.

- **Medical History:**

Must not have a history of major neurobehavioral disorders or developmental disabilities.

- **DESIGN AND PROCEDURES**

- **Design:** Multiple-baseline across-subjects design; participants randomly assigned to varying baseline durations (4–10 sessions).
- **Phases:**
  - **Baseline:** Perception and production of /r/ are probed repeatedly without intervention.
  - **Treatment:** All participants complete 12 sessions of online perceptual training (3x/week, 4 weeks).
  - **Maintenance:** Post-treatment, perception and production are monitored for 3 sessions; no further training.

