Online assessment and enhancement of auditory perception for speech sound errors

Protocol NCT04858035

Document generated 03/17/2021

4.3 Statistical Design and Power: Study 3

In the proposed multiple-baseline across-subjects design with randomization, participants' progress will be tracked continuously across baseline and treatment phases using percent accuracy on the two perceptual tasks described in the main proposal. Accuracy in baseline versus treatment phases of the study will be compared using Koehler and Levin's randomization test [101] as implemented in the R package SCRT [102], with visual inspection as a secondary analysis. Visual inspection will compare the baseline and treatment phases for each participant to identify any differences in level, slope, and variability. In addition, trends will be compared across participants to assess whether changes in performance are temporally linked to the introduction of treatment, to evaluate the immediacy of any such changes, and to examine consistency across participants [119]. The SCRT algorithm will evaluate whether the observed difference in accuracy between baseline and treatment phases is unlikely to occur ($p < .05$) relative to the distribution of differences obtained when a null effect is assumed and the labels "baseline" and "treatment" are randomly assigned in all permutations permitted by the specified multiple-baseline design. If there is a statistically significant effect of treatment, the observed difference will be extreme relative to this distribution. In particular, for a p-value of .05, we would expect to see no more than 5% of estimates from the simulated distribution with absolute values equal to or greater than our observed estimate. In addition to the randomization test, we will calculate standardized effect sizes for each participant (Busk & Serlin's d_2 [103]), comparing their performance in the pre-treatment baseline versus post-treatment maintenance phase and dividing by the pooled standard deviation. These will be used to evaluate, at both individual and group levels, whether the effect of treatment on perceptual accuracy exceeds 1.0, a benchmark commonly accepted to represent the minimum clinically significant effect size [99]. The same effect size measure will be used to compare production accuracy in the first three baseline sessions versus the three post-treatment maintenance phases, to test whether gains in perception transfer to production.

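### The production effect size uses the first three baseline sessions as its starting point, so any change over the remaining 1 to 7 untreated baseline sessions is counted as transfer of training

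*SAP*

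**What the plan says.** The protocol (Design and Procedures) randomizes each child to a baseline of 4 to 10 sessions. During baseline, "Perception and production of /r/ are probed repeatedly without intervention". Then "All participants complete 12 sessions of online perceptual training", and afterwards "Post-treatment, perception and production are monitored for 3 sessions; no further training".

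SAP section 4.3 defines a standardized effect size (Busk and Serlin's d_2) for each child. For perception it is obtained by "comparing their performance in the pre-treatment baseline versus post-treatment maintenance phase and dividing by the pooled standard deviation", with no restriction on which baseline sessions count. For production the SAP says that the same measure will "compare production accuracy in the first three baseline sessions versus the three post-treatment maintenance phases", and gives the purpose as "to test whether gains in perception transfer to production". It gives no reason for the narrower production window and describes no adjustment for a production trend during baseline. The randomization test in the same section is specified for accuracy on the two perceptual tasks.

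**The concern.** Staggered baselines are run so that untreated change can be told apart from change that follows the start of treatment. The production effect size does not use that information. It takes its starting level from the sessions furthest from training and leaves out the later untreated sessions, which are nearer to training.

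Whatever happens to production in those later sessions is then counted as gain. Candidates are growing used to the probe and to online testing, natural improvement, or, in the other direction, fatigue or loss of interest. The two effect sizes, which the SAP calls the same measure, also cover different periods.

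Production is half of the stated objective. Because the randomization test covers perception only, this d_2 is the only production analysis that the SAP specifies.

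**Working it through.** **Plan's own figure.** The SAP gives no calculated figure for production. Its 80% power belongs to the perception randomization test, and this point does not depend on it.

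**Inputs.** Baseline length B = 4 to 10, 12 training sessions and 3 maintenance sessions (protocol, Design and Procedures); first-three window and autocorrelation .25 (SAP 4.3). Assumptions: one production probe per session, B spread evenly over 4–10, no true training effect. Drift is in within-child SD units and its values are assumed.

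**Step 1: sessions left out.** B − 3, so 4 − 3 = 1 up to 10 − 3 = 7.

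**Step 2: interval between window midpoints.** The maintenance sessions are B + 13 to B + 15, with midpoint B + 14.
- First three: midpoint 2, gap B + 12, so 16 (B = 4) to 22 (B = 10).
- Whole baseline: midpoint (B + 1)/2, gap (B + 27)/2, so 15.5 to 18.5.
- Last three: midpoint B − 1, gap 15 for every child.

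**Step 3: steady drift of b per session throughout.** The false gain is gap × b. The excess of first three over last three is (B + 12)b − 15b = (B − 3)b. At b = 0.05:
- First three: 16 × 0.05 = 0.80 to 22 × 0.05 = 1.10.
- Whole baseline: 15.5 × 0.05 = 0.775 to 18.5 × 0.05 = 0.925.
- Last three: 15 × 0.05 = 0.75.
- Excess of first over last: 0.05 to 0.35, mean 4 × 0.05 = 0.20.

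If the drift stops when training starts, the false gain is 2b to 8b with the first three and 1b with the last three.

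**Step 4: familiarisation that levels off.** Take f(t) = 0.5(1 − exp(−(t − 1)/2)). Then f(1), f(2), f(3) = 0, 0.197, 0.316, with mean 0.171. By maintenance f is about 0.500, so the first-three false gain is 0.329 at every B.

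| False gain (SD) | B = 4 | B = 10 | Mean over 4–10 |
|---|---|---|---|
| First three | 0.329 | 0.329 | 0.33 |
| Whole baseline | 0.275 | 0.126 | 0.19 |
| Last three | 0.199 | 0.010 | 0.07 |

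**Step 5: chance that one child's d_2 exceeds 1.0 with no training effect.** The 1.0 threshold is borrowed from perception. Simulated with first-order autocorrelation .25, 40,000 series per B, and SD pooled over the two windows:

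| Scenario | First three | Whole baseline | Last three |
|---|---|---|---|
| No drift | 20% | 15% | 20% |
| Familiarisation (step 4) | 30% | 20% | 22% |
| Drift 0.05 per session | 54% | 47% | 46% |

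**The case against.** Several parts of the opposing case stand.

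- **Direction.** A reader might infer that the window necessarily flatters training. The documents do not support that. They give no production drift rate, a decline would bias the gain downward, and no drift means no bias. The children have persistent errors and production is rated by blinded listeners, so a large spontaneous gain is not obvious, though neither fact excludes one.
- **Baseline length.** A reader might infer that the bias is always largest after the longest baselines. That holds only for change that continues through baseline (step 3). If familiarisation levels off early, the first-three bias is the same for every child (step 4), and it is the last-three bias that varies with B.
- **The 1.0 benchmark.** A reader might infer that production will be judged against it. The SAP ties it to "whether the effect of treatment on perceptual accuracy exceeds 1.0" and states no threshold for production. Step 5 is therefore illustrative, and the window problem does not rest on it.
- **Choice of replacement.** The last three sessions are not clearly the best window. They leave out as many baseline sessions as the first three do, and still differ from the perception window. In step 5 the whole baseline does better with no drift or familiarisation and is about one point worse under steady drift.
- **What remains.** Under a steady drift of 0.05, the last-three window still carries 0.75 of the 0.80–1.10 SD. Any before-and-after d_2 has this weakness.

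The first-three window might be defended as giving each child the same number of observations. The last three do so equally, without the untreated gap.

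**Conclusion.** The point holds in a limited form. The production window leaves 1 to 7 untreated sessions between the starting level and training, without a stated reason and unlike the perception measure, and change over those sessions is read as transfer. Under steady or levelling-off improvement, both alternative windows carry less false gain than the first three sessions.

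Under the assumed scenarios, the amount avoided by moving to the last three sessions averages about 0.26 SD for familiarisation (0.33 − 0.07) and 0.20 SD for steady drift. These sizes rest on assumed drift values, one probe per session and evenly spread baselines; the true size and sign are unknown. This is an inexpensive improvement to the only specified production analysis. It does not show that the planned result will be wrong.

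**What to change.** In SAP section 4.3, replace the first-three baseline window for production with one of the following, chosen before the data are seen:

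- the last three production probes before training starts, which gives every child the same number of observations and the same 15-session interval; or
- the whole pre-treatment baseline, which matches the perception d_2 and uses all the untreated data.

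In either case, report first-three against last-three baseline production for each child as the untreated change. The two windows share sessions when the baseline is shorter than six. State whether any benchmark applies to production. Add that the production d_2 alone is not evidence of a training effect, because drift over the 12 training sessions remains in it.

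**Cost.** One phrase and one descriptive summary. No new data are needed provided that production is probed in the later baseline sessions. The protocol says only that probing is repeated, and the SAP specifies continuous tracking for the perceptual tasks, so the production schedule should be confirmed. The reported production gain may look smaller.
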